5.7.2. Pharmacokinetic/Pharmacodynamic Relationships

Relationships of PK parameters for JNJ-3976, and JNJ-3924, and, optionally, of NA, PegIFN- α 2a and/or JNJ-6379 with selected efficacy and/or safety endpoints may be evaluated and graphically displayed.

Modeling of key PD parameters (eg, HBsAg, HBV DNA) may be performed using population PK/PD. If PK/PD modeling of key efficacy endpoints is performed, treatment effect and possible covariates may be investigated. Other biomarkers may be explored at the sponsor's discretion. If conducted, the results will be presented in a separate report.

5.7.3. Immune Analyses

Descriptive statistics (n, mean, SD, CV, geometric mean, median, minimum, and maximum) may be used to describe the magnitude of the gamma interferon (IFN- γ) T-cell response or the CD4+ and CD8+ T-cell responses (expressing at least 1 cytokine such as interleukin [IL]-2, tumor necrosis factor [TNF]- α or IFN- γ specific to any HBV antigen) as defined by ELISpot and/or ICS, respectively. Changes from baseline (or positivity threshold) may also be tabulated for PBMCs during study intervention and follow-up. The proportion (%) of CHB patients with positive detectable responses based on the magnitude of the IFN- γ T-cell response or the CD4+ or CD8+ T-cells expressing at least 1 of the cytokines amongst IL-2, TNF- α or IFN- γ for 1 of the HBV antigens as defined by ELISpot and/or ICS, respectively, may be determined. Other immune cells, such as NK-cells, MDSCs, DCs, and B-cells, may be evaluated/explored.

Changes from baseline (or positivity threshold) in HBV-specific peripheral blood T-cell responses may be summarized and tabulated.

Graphs showing the individual subject values as dots, together with horizontal lines indicating the corresponding median and interquartile range (IQR) per time point for each assay may be presented. The spaghetti plots may be used to show the patient profiles per time point for each assay. A graph showing the median and IQR over time may be presented. A bar chart may be used to show the breadth of response (i.e. HBV-specific immune response rate for combinations of peptide pools).

For intracellular cytokine staining (ICS), for all cytokine combinations (IFN γ and/or TNF α and/or IL-2), pie charts may be presented to reflect the distribution of each of the cytokine combinations (i.e. the proportion of a specific cytokine combination of the CD4 or CD8 T-cells secreting at least one cytokine), and bar charts may be presented to reflect the mean magnitude of each combination.

5.7.4. Viral Genome Sequence Analysis

Viral genome sequence analysis may be performed to identify pre-existing baseline polymorphisms and to evaluate emergence of genetic variations (including substitutions) associated with JNJ-56136379, JNJ-3989, and/or ETV or TD treatment on both nucleotide and/or amino acid level.

The sequencing of samples may be triggered by the sponsor virologist based on changes in HBV DNA levels observed in each individual participant and the limits of the sequencing assay.

Virology results will be presented by specified timepoints and genetic region and position of interest. A separate virology report may be prepared.

5.7.5. Definition of Subgroups

5.7.5.1. Subgroups for Efficacy Analyses

Table 8: Subgroups for efficacy analyses

Subgroup	Definition
Sex	Male, Female
Age Group	≤ 45 years, > 45 years
Race	Asian, Non-Asian
Geographical region	Asia, Europe, Oceania
Type of NA at baseline	TeD, TAF, ETV
HBsAg level at baseline	$< 1,000$ IU/mL; $\geq 1,000$ IU/mL- $< 10,000$ IU/mL; $\geq 10,000$ IU/mL
HBeAg at baseline	Positive, Negative

5.7.5.2. Subgroups for Safety Analyses

Table 9: Subgroups for safety analyses

Subgroup	Definition
Sex	Male, Female
Age Group	≤ 45 years, > 45 years
Race	Asian, Non-Asian
BMI at Baseline	Underweight < 18.5 , Normal ≥ 18.5 - < 25 , Overweight ≥ 25 - < 30 , and Obese ≥ 30
Type of NA at Baseline	TeD, TAF, ETV

5.8. Interim Analyses and Data Review Committee

5.8.1. Data Review Committee

The internal DRC will conduct periodic data review to ensure the continuing safety of the study participants during the entire course of the study. The DRC will also review the results of the

primary and interim analyses (IAs) comprising cumulative safety and selected efficacy endpoints for providing the sponsor with further insight and interpretation of the data. Details on the roles and responsibilities of the DRC, as well as data reviews and the flows of communication, are documented in the DRC charter. Description of the DRC is provided in Section 9.6 of the Master Protocol PLATFORMPAHPB2001.

5.8.2. Independent Flare Expert Panel

An IFLEP is appointed. The IFLEP is composed of 3 independent medical experts with experience and expertise in HBV and its treatment. The IFLEP will monitor ALT flares and will make recommendations regarding flare management based on an analysis of aggregate data.

In order to allow for an unbiased assessment, members of the committee will not serve as study investigators or as members of the DRC.

Further details on the IFLEP process will be included in the IFLEP charter.

5.8.3. Data Reviews and Interim Analyses

The DRC will conduct periodic safety data reviews (DRs) to ensure the continuing safety of the study participants during the entire course of the study.

5.8.3.1. Data Reviews

The DRC will periodically review unblinded cumulative safety and efficacy data at the following timepoints:

- DR1: 20 participants have reached the Week 12 (end of treatment period 1) time point or discontinued earlier.
- DR2: 20 participants have reached the Week 16 time point or discontinued earlier.
- DR3: 20 participants have reached the FU Week 12 time point or discontinued earlier.
- DR4: 20 participants have reached the FU Week 48 time point or discontinued earlier.

Safety data comprising AEs, SAEs, AEs of special interest, laboratory data, electrocardiogram (ECG) data and any other data applicable for the study, will be summarized, plotted and provided as appropriate.

Besides the safety variables listed above, selected efficacy parameters for review may include values and changes from baseline over time in HBV disease blood markers (such as HBsAg, HBeAg, HBV DNA and ALT), proportion of participants with virologic breakthrough, and flares.

5.8.3.2. Interim Analyses

Interim analyses (IAs) will be conducted—to assess safety and efficacy to support the sponsor’s interactions with health authorities, as well as to inform internal decisions about additional studies and/or investigation of other treatment combinations. The IAs are planned when all:

- Approximately 20 participants have completed Week 24 (EOSI) or discontinued earlier.

- All participants have completed Week 36 (FU Week 12) or discontinued earlier.
- All participants have completed Week 48 (FU Week 24) or discontinued earlier.
- An optional IA may be conducted when all participants have completed Week 60 (FU Week 36) or discontinued earlier.

The primary analysis will be conducted at the time when all participants have completed Week 24 or discontinued earlier.

Both primary and interim analyses will be based on all data available at the prespecified cut-off time points and may include data at later time points for those participants who have reached subsequent visits.

The final analysis will be performed when all participants have completed the last study visit (FU Week 48) or discontinued earlier.

5.8.3.3. Analysis Overview of Data Reviews, Interim, Primary and Final Analyses

The overview of data domains and specific endpoints that will be provided to the DRC for review is presented in [Table 10](#). Details on the type of summaries and analyses of both efficacy and safety variables are described in the following sections.

Table 10: Overview of Data Summaries and Analyses to be Provided to the DRC at Data Reviews, Interim, Primary and Final Analyses

	DR1/ Week 12 (N=20)	DR2/ Week 16 (N=20)	IA1/ Week 24 (N=20)	DR3 / FU Week 12 (N=20)	Prima ry Analy sis/ Week 24 (N=50)	IA2/ FU Week 12 (N=50)	IA3 / FU Week 24 (N=50)		DR4 / FU Week 48 (N=20)	IA4 / FU Week 36 (N=50) (optional)	Final Analysi s/ FU Week 48 (N=50)
Subject Information											
Baseline & Demographic characteristics	X	X	X	X	X	X	X		X	X	X
Disposition and Study Populations	X	X	X	X	X	X	X		X	X	X
Extent of Exposure	X	X	X	X	X	X	X		X	X	X
Safety											
TEAEs, SAEs, AE of interest, fatal AEs, AEs causing treatment discontinuation	X	X	X	X	X	X	X		X	X	X
Laboratory Tests	X	X	X	X	X	X	X		X	X	X
ECG	X	X	X	X	X	X	X		X	X	X
Vital signs	X	X	X	X	X	X	X		X	X	X
Efficacy											
Values and Changes over time in HBsAg, HBeAg, HBV DNA and ALT	X	X	X	X	X	X	X		X	X	X
Proportion of participants with a reduction of at least 2 log ₁₀ IU/mL in HBsAg levels from baseline over time	X	X	X	X	X	X	X		X	X	X
Proportion of participants with HBsAg, HBeAg, HBV DNA, and ALT below/above different cutoffs	X	X	X	X	X	X	X		X	X	X
Other secondary efficacy endpoints			X	X	X	X	X		X	X	X
Exploratory endpoints			X	X	X	X	X		X	X	X
Virologic breakthrough	X	X	X	X	X	X	X		X	X	X
Flares: Viral, Biochemical, Clinical	X	X	X	X	X	X	X		X	X	X
PK*	X	X	X	X	X	X	X		X	X	X
*If there are available data, it will be analyzed.											

6. SUPPORTING DOCUMENTATION

6.1. Appendix 1 List of Abbreviations

AE	adverse event
ALT	alanine aminotransferase
AST	aspartate aminotransferase
ATC	anatomic and therapeutic class
AUC	area under the curve
BMI	body mass index
BUN	blood urea nitrogen
CHB	chronic hepatitis B
CI	confidence interval
C _{max}	maximum concentration
CPK	creatinine phosphokinase
CRF	case report form
CSR	Clinical Study Report
CV	coefficient of variation
DAIDS	division of acquired immunodeficiency syndrome
DR	data review
DRC	Data Review Committee
ECG	electrocardiogram
eCRF	electronic case report form
eGFR	estimated glomerular filtration rate
eGFR _{cr}	estimated glomerular filtration rate calculated based on Creatinine
eGFR _{cys}	estimated glomerular filtration rate calculated based on Cystatin C
EOS	end of study
EOT	end of treatment
ETV	entecavir
FAS	full analysis set
FC	functional cure
FEPO ₄	urine fractional excretion of phosphate
FU	Follow-up
GGT	Gamma-glutamyltransferase
HBcrAg	hepatitis B core-related antigen
HB _e	hepatitis B envelope
HB _s	hepatitis B surface
HB _e Ag	hepatitis B envelope antigen
HB _s Ag	hepatitis B surface antigen
HBV	hepatitis B virus
HBV DNA	hepatitis B virus deoxyribonucleic acid
HBV RNA	hepatitis B virus ribonucleic acid
IA	Interim analysis
ICH	International Conference on Harmonisation
ICS	intracellular cytokine staining
IFLEP	Independent Flare Expert Panel
IFN-FAS	Interferon-Full Analysis Set
IQR	Interquartile range
ISR	injection site reaction
IU/mL	international units per milliliter
KPD	kinetic pharmacodynamic model
LDh	lactic acid dehydrogenase
LOQ	lower limit of quantification
LOCF	last observation carried forward
LOD	limit of detection
LSM	liver stiffness measurements
MedDRA	Medical Dictionary for Regulatory Activities

mFAS	modified full analysis set
MH	Mantel Haenszel
NA	nucleos(t)ide analogs
NGS	next generation sequencing
PBMC	peripheral blood mononuclear cell
PD	pharmacodynamic(s)
PegIFN- α 2a	pegylated interferon alpha-2a
PI	principal investigator
PK	pharmacokinetic(s)
PoC	Proof of Concept
QTc	corrected QC interval
QTcF	QT interval corrected for heart rate according to Fridericia
RBP	retinol binding protein
RR	Interval between R wave of one heartbeat and R wave of preceding heartbeat
RT	Reference Timepoint
SAE	serious adverse event
SAP	Statistical Analysis Plan
SCr	serum creatinine
SD	standard deviation
SMQs	standardised MedDRA queries
SPO4	serum phosphate
TAF	tenofovir alafenamide
TEAE	treatment-emergent adverse event
TD	Target detected
TeD	tenofovir disoproxil
Tmax	time to maximum concentration
TND	target not detected
TNF	tumor necrosis factor
TSH	thyroid stimulating hormone
T4	thyroxine
UACR	urine albumin to creatinine ratio
UCr	urine creatinine
ULN	Upper limit of normal
UPCR	urine protein to creatinine ratio
WBC	white blood cell
WHO-DD	World Health Organization Drug Dictionary

6.2. Appendix 2 Changes to Protocol-Planned Analyses

There are no changes to the protocol-planned analyses.

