Relationships of PK parameters for JNJ-3976 and JNJ-3924, and, optionally, of NA, PegIFN- α 2a and/or JNJ-6379 with selected efficacy and/or safety endpoints may be evaluated and graphically displayed.

Modeling of key PD parameters (eg, HBsAg, HBV DNA) may be performed using population PK/PD. If PK/PD modeling of key efficacy endpoints is performed, treatment effect and possible covariates may be investigated. Other biomarkers may be explored at the sponsor's discretion. If conducted, the results will be presented in a separate report.

Immune Analyses

Descriptive statistics (n, mean, SD, CV, geometric mean, median, minimum, and maximum) will be used to describe the magnitude of the IFN- γ T-cell response or the CD4+ and CD8+ T-cell responses (expressing at least 1 cytokine such as IL-2, TNF- α or IFN- γ specific to any HBV antigen) as defined by ELISpot and/or ICS, respectively. Changes from baseline (if present) will also be tabulated for PBMCs during study intervention and follow-up. The proportion (%) of CHB patients with positive responses based on the magnitude of the IFN- γ T-cell response or the CD4+

or CD8+ T-cells expressing at least 1 of the cytokines amongst IL-2, TNF- α or IFN- γ for 1 of the HBV antigens as defined by ELISpot and/or ICS, respectively, will be determined. Other immune cells, such as NK-cells, MDSCs, DCs, and B-cells, may be evaluated/explored.

Pharmacogenomic Analyses

The statistical approach for analyzing the exploratory host DNA research, including epigenetic analyses, may depend on the objective of the analyses (eg, efficacy, safety, and/or PK) and possibly relevant genes at the time of analysis. Analyses will be conducted at the sponsor's discretion, will always be under the sponsor's supervision, and results will be presented either in the clinical study report or a separate report.

Host Biomarker Analyses

Statistical approaches to explore correlations between clinical outcome and blood biomarkers vary and depend on the different data types of the applied technology platforms, as well as on the extent of observed interindividual variability. Analyses will be conducted at the sponsor's discretion, will always be under the sponsor's supervision, and results will be presented either in the clinical study report or a separate report.

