9.5. Interim Analyses

Interim analyses (IAs) will be conducted to assess safety and efficacy to support the sponsor's interactions with health authorities, as well as to inform internal decisions about additional studies and/or investigation of other treatment combinations. The IAs are planned when:

- Approximately 20 participants have completed Week 24 (EOSI) or discontinued earlier
- All participants have completed Week 36 (FU Week 12) or discontinued earlier
- All participants have completed Week 48 (FU Week 24) or discontinued earlier.

An optional IA may be conducted when all participants have completed Week 60 (FU Week 36) or discontinued earlier.

The study is open-label, and the sponsor will conduct the pre-planned IAs. Hence, the study team and the DRC will have access to the IA results, while the investigators and participants will not.

Both primary and interim analyses will be based on all data available at the pre-defined cut-off time points, and may include data at later time points for those participants who have reached subsequent visits.

More details are provided in Section 9.5 of the Master Protocol PLATFORMPAHPB2001.

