6.4.	Appendix 4 Protocol Deviations	71
6.5.	Appendix 5 Prior and Concomitant Medications	72
6.6.	Appendix 6 Medical History	73
6.7.	Appendix 7 Intervention Compliance	74
6.8.	Appendix 8 Adverse Events of Special Interest.....	75
6.9.	Appendix 10 Laboratory Toxicity Grading.....	80

7. REFERENCES..... 81

VERSION HISTORY

Document History	
Document	Date
Original SAP	30 June 2021
Amendment 1	15 October 2021
Amendment 2	18 May 2023

Amendment 2 (this document)

Overall rationale of this Amendment:

This is an administrative amendment that incorporates additional clarifications on endpoints, data handling rules, and updates to descriptive analyses that were previously documented in the Data Presentation Specifications.

Clarifications, Additions, Corrections		
Section Number and Name	Description of Change	Rationale
Section 5.1.9. Data Handling Rules	Revised ULOQ and Imputed Values data cutpoints for HBsAg, HBeAg and HBcrAg. Updated guidelines for the imputation of HBV DNA.	Improved language for clarity and precision.
Section 5.1.10. Main Groups for Analysis Section 5.3.2. Analysis Methods Section 5.4.2. Analysis Methods Section 5.5.2. Analysis Methods Section 5.6. Safety Analyses	Analyses will be focused on all subjects, and some analyses will be performed by group.	Change in the scope of the analysis.
Section 5.4.1.1.2 NA Re-Treatment Criteria During FU Section 5.4.2.1.2.1. NA Re-Treatment Criteria During FU	Removed NA re-treatment sub-criteria analysis.	NA re-treatment sub-criteria was not collected in CRF.

Clarifications, Additions, Corrections		
Section Number and Name	Description of Change	Rationale

Section 5.4.1.1.12. ALT Normalization
 
Section 5.4.2.1.8. HBeAg Seroconversion
 
Section 5.5.2.2.3. Anti-HBs Antibodies
	Removed an analysis.	
Majority of participants had ALT values within normal range at baseline.
 
HBeAg seroclearance is defined only for participants who were HBeAg positive at baseline.
 
Qualitative anti-HBs results are not collected.

Section 5.4.1.1.15. Flares	For on and off treatment biochemical flare definitions, nadir definition is updated to the lowest value observed up to the start of the flare.	The nadir definition was updated to include screening visit.
Section 5.4.2.1.10. Suppressed HBV DNA	Added two thresholds HBsAg and HBV DNA thresholds.	Additional analyses for HBsAg and HBV DNA thresholds were decided to be performed

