
Section 5.4.2.1.10. Suppressed HBV DNA
 
Section 5.4.2.2.1. HBsAg, HBeAg, HBV DNA and ALT
 
Section 5.5.1.4.1. Association Between Baseline Characteristics/Viral Blood Markers and Selected Efficacy Variables
 
Section 5.5.2.2.3. Anti-HBs Antibodies
	Added to text to avoid analyses in case of insufficient data.	Improved language for clarity.
Section 5.4.2.2.1. HBsAg, HBeAg, HBV DNA and ALT	Clarification of text.	Typographical corrections.

Section 5.4.2.2.1. HBsAg, HBeAg, HBV DNA and ALT
 
Section 5.5.2.2.1. Liver Stiffness Measurement
	Specified time points for the analysis and removed HBV DNA from the scope.	Clarification of text.

Clarifications, Additions, Corrections		
Section Number and Name	Description of Change	Rationale
Section 5.5.2.2.2. HBV RNA and HBcrAg		
Section 5.5.1.3.4. Time to Appearance of Anti-HBe Antibodies	Updated text for time to appearance of anti-HBe antibodies analysis which will be performed only for anti-HBe negative participants at study entry.	Improved language for clarity and precision.
Section 5.5.1.5. Sustained HBsAg Response Section 5.5.2.5. Sustained HBsAg Response	Added section with definitions of HBsAg sustained response and their analyses.	Additional analysis for HBsAg was included to better characterize off-treatment HBsAg response.
Section 5.5.2.2.3. Anti-HBs Antibodies	Removed cross-tabulation evaluation for anti-HBs.	Qualitative results for anti-HBs antibodies were not collected.
Section 5.7.3. Immune Analyses	Removed some analyses.	Change in the scope of the analysis.
Section 5.7.4. Viral Genome Sequence Analysis	Removed subsections.	Subsections were removed to simplify the analysis.
Section 5.7.5.1. Subgroups for Efficacy Analyses	Removed some subgroups.	Remaining subgroups are sufficient for the scope.
Appendix 8 Adverse Events of Special Interest	Updated preferred terms.	MedDRA was updated from v23.0 to v25.1.
Appendix 9 Medications of Interest	Removed the medications of special interest section.	Removal due to discontinuation of JNJ-6379.

Amendment 1

Overall rationale for the Amendment:

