1.1. Objectives and Endpoints

Objectives	Endpoints
Primary	

 To evaluate the efficacy in terms of HBsAg levels of the study intervention (i.e. JNJ-3989 + JNJ-6379^d + NA and PegIFN-α2a). 	
 Proportion of participants with a reduction of at least 2 log₁₀ IU/mL in HBsAg levels from baseline to Week 24 (end of study intervention [EOSI]).
Secondary	

 To evaluate the safety and tolerability of the study intervention. 	
 Safety and tolerability including but not limited to the proportion of participants with (serious) adverse events (S)AEs and abnormalities in clinical laboratory tests (including hematology, blood biochemistry, blood coagulation, urinalysis, urine chemistry, and renal biomarkers), 12-lead electrocardiograms (ECGs), vital signs, and ophthalmic and physical examinations throughout the study.

 To evaluate the efficacy of the study intervention at the end of the 24-week treatment period. 	
 Proportion of participants meeting the protocol-defined NA treatment completion criteria at EOSI.

 To evaluate the efficacy of the study intervention as measured by blood markers (such as HBsAg, HBeAg^a, HBV DNA, and alanine aminotransferase [ALT]) during the study intervention and follow-up (FU) period. 	
 Proportion of participants with HBeAg^a, HBsAg, HBV DNA, and ALT levels below/above different cut-offs. Proportion of participants with HBsAg and/or HBeAg^a seroconversion.

Objectives	Endpoints
	
 Change from baseline over time in HBsAg, HBeAg^a, and/or HBV DNA. Time to achieve HBsAg and/or HBeAg^a seroclearance/seroconversion, and/or HBV DNA < lower limit of quantification (LLOQ).

 To evaluate the frequency of virologic breakthrough^b during the 24-week treatment period, as well as during the FU period for participants who continue treatment with NA. 	
 Proportion of participants with virologic breakthrough^b.

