5.6.3.5. Physical and Ophthalmic Examinations

The physical and ophthalmic examination findings and abnormalities will be listed. A listing of participants who experienced a decrease or loss of vision at any timepoint during study will be provided.

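### SAP Appendix 2 declares no departures from the protocol, but ophthalmic and physical examination abnormalities are only listed, T-cell summaries became optional, and an added HBsAg analysis is not declared there

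*SAP*

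**What the plan says.** **The declaration.** SAP 6.2 (Appendix 2) consists of one sentence: "There are no changes to the protocol-planned analyses".

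**Examinations.** Protocol Section 3 and SAP 1.1 define the same secondary safety endpoint. It covers the proportion of participants with adverse events and with abnormalities in several domains, ending with "vital signs, and ophthalmic and physical examinations throughout the study". Protocol 9.4.3 plans descriptive summaries and names physical examinations among them. SAP 5.6.3.5 says: "The physical and ophthalmic examination findings and abnormalities will be listed". It adds one further listing, of participants with reduced or lost vision.

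**T-cell responses.** Change from baseline in HBV-specific T-cell responses is an exploratory endpoint in both documents. Protocol 9.4.4 says: "Changes from baseline (if present) will also be tabulated for PBMCs during study intervention and follow-up". SAP 5.7.3 says: "Changes from baseline (or positivity threshold) in HBV-specific peripheral blood T-cell responses may be summarized and tabulated".

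**Sustained HBsAg response.** SAP 5.5.1.5 gives four definitions. The Version History for Amendment 2 records: "Added section with definitions of HBsAg sustained response and their analyses".

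**The concern.** Appendix 2 is where a reader of the study report looks to see whether the analysis departed from the protocol. If it says nothing changed, that reader has no reason to compare the texts.

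The examination component matters most. Protocol 2.3.2.1 names ophthalmologic disorders among the established PegIFN-α2a risks, and Protocol 7.1 makes new or worsening ones a reason to stop that drug. The Schedule of Activities provides examinations at screening and Week 24, and at Week 8 for some participants with risk factors. The data will exist, but no planned output turns them into the proportion that the endpoint promises.

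The other two items concern interpretation. An exploratory summary that may or may not be produced can be dropped after the results are known. An added efficacy derivation that Appendix 2 does not mention may be taken for a protocol analysis by a reader who does not consult the Version History.

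**Working it through.** The plan gives no figure for this point, so the check is mainly a comparison of texts.

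**1. Safety domains named in the endpoint and the output planned for each**

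| Domain | SAP section | Planned output for abnormalities |
|---|---|---|
| Laboratory tests | 5.6.3.1 | number and percentage of participants, by phase |
| ECG | 5.6.3.3 | number and percentage, by phase |
| Vital signs | 5.6.3.4 | number and percentage, by phase |
| Physical examination | 5.6.3.5 | listing only |
| Ophthalmic examination | 5.6.3.5 | listing only |

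The general rule in SAP 5.6, that categorical data are summarised by frequencies and percentages, does not clearly close the gap, because the section specific to these examinations plans listings and nothing else.

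**2. What a count would add.** With 0 events in n participants, the one-sided 95% upper limit is 1 − 0.05^(1/n).
- n = 50 (all planned participants examined): 1 − 0.05^(1/50) = 0.058.
- n = 40 (an assumed number of PegIFN-α2a recipients; the documents give none): 1 − 0.05^(1/40) = 0.072.

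So even a clean result would be compatible with a rate of about 6% to 7%. A listing with no denominator does not convey this. The figures are illustrations, not predictions.

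**3. T-cell summaries.** Protocol 9.4.4 uses *will* for the descriptive statistics, the change from baseline and the proportion with a positive response. SAP 5.7.3 uses *may* for all three. The Amendment 2 log records that some immune analyses were removed because the scope changed. Appendix 2 does not mention it.

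**4. Sustained HBsAg response.** SAP 5.5 refers to Section 1.1 for the exploratory endpoints. Neither SAP 1.1 nor Protocol Section 3 contains sustained response.

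On timing, the documents give two anchor dates:
- Protocol Amendment 3: 04 October 2021.
- SAP Amendment 2: 18 May 2023, which is 591 days (591/7 = 84.4 weeks) later.

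Day 1 to FU Week 48 is 24 + 48 = 72 weeks, or 504 days. A participant with Day 1 on 04 October 2021 was due at FU Week 24 on 05 September 2022 and at FU Week 48 on 20 February 2023. The latter is 591 − 504 = 87 days before SAP Amendment 2. Anyone already on treatment at Protocol Amendment 3 was due even earlier.

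On access, Protocol 8.1 sends HBsAg results to the sponsor throughout this open-label study, and Protocol 9.5 says "the study team and the DRC will have access to the IA results". Another Amendment 2 rationale cites collected data: "Majority of participants had ALT values within normal range at baseline". No document dates an interim analysis or a database lock, or says how many participants had reached a given visit.

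**5. Another undeclared difference.** Protocol 9.4.2.1 applies the primary-endpoint method to PegIFN-α2a recipients without condition. SAP 5.3.2 does so only if the analysis sets differ by at least 2 participants. The numerical effect is negligible, but it is a change. SAP Section 4 also adds pandemic-modified analysis sets that are not in Protocol 9.3.

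**The case against.** **The Master Protocol may plan listings.** Protocol 9.4.3 refers to Master Protocol 9.4.3, which is not among the documents. The list of descriptive summaries in Protocol 9.4.3 also omits ophthalmic examinations. This stands as a limit on what can be said about method. It does not remove the mismatch, because SAP 1.1 keeps a proportion as the endpoint and SAP 5.6.3.5 does not produce it.

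**Ophthalmic events are counted elsewhere.** A reader might infer that ophthalmic safety has no rate at all. That goes too far. SAP 5.6.2 tabulates adverse events, including those leading to discontinuation of an agent, with number and percentage. What stays uncounted is an examination abnormality not reported as an adverse event, and the endpoint names the two separately.

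**Sustained response is not concealed.** A reader might infer that it is presented as if planned. The Version History dates it and calls it an additional analysis, it sits under exploratory endpoints, and Protocol 9.4.2 allows additional hypothesis-generating analyses of the primary and selected secondary endpoints. The defect is only that Appendix 2 is silent and that its status relative to the data is not stated.

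**Data access is not proven.** A reader might infer that the definitions were written after HBsAg outcomes were seen. The dates and the open-label design make this likely. But the ALT rationale concerns baseline values only, and Amendment 2 says it carries content already documented in the Data Presentation Specifications, which are not available. The definitions could predate 18 May 2023.

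**Selective highlighting is constrained.** SAP 5.5.2.5 already plans a table for each definition that at least one participant meets, and plots for each. Definition 4 sorts participants into decreasing, stable or increasing levels; it is not a rival responder rule.

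**The immune change is partly disclosed** in the Version History, and the endpoint is exploratory and from selected sites.

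**Conclusion.** The Appendix 2 statement is inaccurate and should be replaced. The firmest ground is the examination component: if the SAP is followed as written, one component of a secondary safety endpoint has no count or percentage, although comparable domains do. The shift from *will* to *may* for T-cell summaries is a second undeclared change. Sustained HBsAg response is a late, openly logged, exploratory addition that Appendix 2 should identify; its post hoc status is probable but not established.

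The consequences are limited. The study is exploratory with no formal hypothesis, and no planned efficacy estimate changes. Safety analyses are descriptive and no confidence interval is specified for the other safety domains, so n (%) is enough here.

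This rests on two assumptions: that examination abnormalities are recorded so that participants can be counted, which the planned listing implies, and that Master Protocol 9.4.3 does not redefine the endpoint.

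**What to change.** - **SAP 5.6.3.5.** Add n (%) of participants with a new or worsened ophthalmic abnormality versus screening at any post-baseline examination (Week 8, Week 24 and unscheduled), for PegIFN-α2a recipients and for all participants. Counting Week 24 alone would miss the Week 8 and prompt vision-loss examinations described in the Schedule of Activities and Protocol 8.2.5. Add n (%) with a new post-baseline physical examination abnormality by analysis phase. State the number examined as denominator. A confidence interval is optional. Keep the listings.
- **SAP 5.7.3.** Restore *will* for the T-cell change-from-baseline summaries on the available samples, or declare the change.
- **SAP Appendix 2.** Replace the sentence with the actual departures, including the conditional use of the PegIFN-α2a set and the added pandemic-modified sets. Identify sustained HBsAg response as a non-protocol exploratory analysis added in Amendment 2 (18 May 2023). State whether HBsAg follow-up data had been seen when it was defined and, if so, label it post hoc.

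The cost is two small tables and some SAP wording, with no new data. The downside is that sustained-response results may carry a post hoc label.
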